# 4.4.2 Exploratory Outcomes (Imaging)

X-rays are evaluated for Kellgren-Lawrence (K-L) grade and absence of severe osteoarthritis by the central laboratory for confirmation of eligibility.

Post-injection X-rays taken at 12 months will receive K-L grades that will be compared to baseline. For each subject, results will be categorized as (1) worse—a higher Kellgren-Lawrence grade at 12 months compared to baseline, (2) no change in grade from baseline to 12 months or (3) Improvement—a decrease in grade from baseline to 12 months. An analysis of the percentage of subjects in each treatment group who fall into each of these three categories will be done using a Likelihood Ratio Chi-square test. This test will also be repeated within subgroups defined by the baseline K-L grade.

Measurements of medial and lateral Joint Space Width (JSW) will be performed to assess narrowing over time in the medial and lateral compartments of the treated joint. Joint Space Narrowing (JSN) will be calculated for each compartment as the change in JSW between the 12 Month visit and the Baseline visit.

A list of planned statistical tests on imaging data is presented in **Table 6**. All tests will be conducted at  $\alpha$  = 0.05 and will not be adjusted for multiple comparisons as these are exploratory outcomes. In addition to these tests, logistic regression will be used to determine whether imaging results are associated with OMERACT-OARSI categorization.

Variable	Test
X-ray	
Change in K-L	Likelihood Ratio Chi-Square
Change in K-L by baseline K-L grade	Likelihood Ratio Chi-Square for each subgroup

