An X-ray will be obtained at 12 months and annually thereafter to assess anatomical changes. Only radiograph images taken up to 24 months of follow-up will be transferred to the Core Imaging Laboratory for independent review. Image acquisition, transfer, and analysis procedures will be performed using validated, prospectively defined methods. All AEs that occur during the 12 month blinded study period will be recorded. In the long-term follow-up phase (12 - 60 months), only events of interest will be recorded.

After each subject completes all 12-month follow-up evaluations, only subjects will be blinded to the individual treatment allocation resulting in single-blind design following 12-month follow-up time point. Subjects from both groups will be able to request additional injections of their originally assigned treatment as frequently⁴ as needed, provided they did not experience any significant clinical concerns after previous treatment administrations and are benefiting from it, as determined by the investigator. During the long-term follow-up phase (12 - 60 months), subjects may also elect to cross over to the other treatment arm and receive additional injections of the other treatment as frequently as needed, provided they did not experience any significant clinical concerns after previous treatment administrations and are benefiting from it, as determined by the investigator. Subjects may only cross over from their originally assigned treatment group to the other treatment group one time during the study. Subjects seeking alternative invasive OA treatment in the index knee who do not wish to cross over or who have already crossed over will exit the study, and their selected treatment option will be recorded.

⁴ Please refer to Synvisc One IFU for specified clinical use requirements.

Study Duration:	Maximum study duration per subject is 62 months: 60 r	nonths from
	treatment to last follow-up, and two additional mo	onths if the
	maximum visit window time is realized.	
Inclusion Criteria:	1. Male or female at least 18 years of age at time of	f screening.
	2. Willingness and ability to comply with study proc	cedures and
	visit schedules and able to follow oral a	and written
	instructions.	
	3. A standing knee radiograph showing a K-L gra	de of 2 to 4
	and an absence of severe osteoarthritis	defined as
	advanced stage osteoarthritis, including large o	steophytes,
	chronic fractures or bone remodeling, severe	deformity or

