	never) to 4 (extreme or always). A higher score indicates worse
	pain, stiffness, or functional limitation.
	The EuroQol-5 Dimensions
	The EuroQol-5 Dimensions (EQ-5D) is a validated instrument
	which assesses an individual's current health status and heath
	related quality of life. The EQ-5D-3L descriptive component
	assesses five dimensions: mobility, self-care, usual activities,
	pain/discomfort, and anxiety/depression over three levels of
	severity. The EQ visual analogue scale (EQ VAS) assesses the
	respondent's self-rated overall health state on a scale from 0 (worst
	imaginable health state) to 100 (best imaginable health state).
	Numeric Rating Scale
	The NRS is a validated measure of knee pain. The NRS is an 11
	point Likert type scale anchored by 0 "no pain" and 10 "worst
	possible pain". Subjects rate their average pain over the last 48
	hours.
	Patient Preference Questionnaire
	Patient preferences are concerned with determining patient-related
	factors such as patients' adherence to treatment, patients'

	satisfaction with treatment, and health outcomes. Patient
	preferences will be measured utilizing questions to elicit patients'
	preferences following their knee OA treatment.
	Resource Utilization and Costing
	Health economics will be evaluated throughout the study.
	Healthcare resource utilization for each subject will be recorded to
	capture information about healthcare costs following index
	treatment with nSTRIDE APS or HA and follow-up.
Imaging	Radiographs
Assessment	Standing posterior-anterior (PA) fixed flexion knee radiographs (X-
Tools:	rays) are used to assess structural features of the joint, including
	joint space width, and presence or absence of subchondral
	sclerosis, subchondral cysts, and osteophytes. X-ray assessments
	will be performed by a core imaging laboratory.
Primary Endpoint:	The primary endpoint will be the change in pain from baseline to 12
	months following injection of nSTRIDE APS or HA, as measured by
	the WOMAC LK 3.1 pain subscale.
Primary Hypothesis	H ₀ : μ _{APS} = μ _{HA} vs H ₁ : μ _{APS} ≠ μ _{HA}
Primary Hypothesis for nSTRIDE	H ₀ : μ _{APS} = μ _{HA} vs H ₁ : μ _{APS} ≠ μ _{HA}
Primary Hypothesis for nSTRIDE Superiority Testing:	H ₀ : $\mu_{APS} = \mu_{HA} vs H_1: \mu_{APS} \neq \mu_{HA}$ Where:
Primary Hypothesis for nSTRIDE Superiority Testing:	H ₀ : $\mu_{APS} = \mu_{HA} vs H_1: \mu_{APS} \neq \mu_{HA}$ Where: H ₀ is the Null Hypothesis

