# 4.4 Exploratory Outcomes (Phase I)

#### 4.4.1 Questionnaire Data

Exploratory objectives of this study include determining whether nSTRIDE APS is superior to HA with regard to the endpoints in **Table 5**. Where repeated measures tests are statistically significant, tests at individual time

points will be performed. All tests will be conducted at  $\alpha$  = 0.05 and will not be adjusted for multiple comparisons as these are exploratory outcomes.

Exploratory Outcomes	Test	Expected Outcome
Mean NRS Pain Δ (1, 3, 6 Months)	Repeated Measures ANOVA	Trend APS Superior
Mean WOMAC Pain ∆ (Percent change from baseline to12 Month)	T-Test or WMW	APS Superior
Mean WOMAC Function Δ (Percent change from baseline to12 Month)	T-Test or WMW	APS Superior
Mean WOMAC Function changes over time within treatment	Repeated measures ANOVA	Significant change from baseline
Mean EQ-5D ∆ Global Assessment VAS (12 Month minus Baseline)	T-Test or WMW	APS Superior
Mean EQ-5D Δ Global Assessment VAS (Percent change from baseline to12 Month	T-Test or WMW	APS Superior
Mean EQ-5D Global Assessment VAS changes over time within treatment	Repeated measures ANOVA	Significant change from baseline
Mean EQ-5D *∆ Single Index Value (12 Month minus Baseline)	T-Test or WMW	APS Superior
Mean EQ-5D ∆ Single Index Value (Percent change from baseline to12 Month	T-Test or WMW	APS Superior
Mean EQ-5D Single Index Value changes over time within treatment	Repeated measures ANOVA	Significant change from baseline

 Table 5 – Planned Exploratory Analyses, Questionnaire Data

Exploratory Outcomes	Test	Expected Outcome
EQ-5D Dimensions (Mobility, Self-Care, Usual Activities, Pain/Discomfort, Anxiety/Depression) (12 Month)	Likelihood Ratio Chi-Square	APS Superior
Mean WOMAC Pain ∆ (1, 3, & 6 Months)	Repeated Measures ANOVA or Friedman Test	Trend APS Superior
Mean WOMAC Function Δ (1, 3, & 6 Months)	Repeated Measures ANOVA or Friedman Test	Trend APS Superior
MCID WOMAC Function Responder (1, 3, & 6 Months)	Fisher's Exact Family α = 0.05	Trend APS Superior
MCID WOMAC Pain Responder (1, 3, & 6 Months)	Fisher's Exact Family α = 0.05	Trend APS Superior
OMERACT-OARSI Responder / Non-responder** (1, 3, 6 & 12 Months) **Traditional published criteria; i.e. not including multiple restricted/ rescue medication usage between 6-12 months	Fisher's Exact Family α = 0.05	Trend APS Superior
Total Mean WOMAC Δ (1, 3, & 6 and 12 Months)	Repeated Measures ANOVA or Friedman Test	Trend APS Superior

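### EQ-5D-3L dimensions and K-L change are ordered outcomes, but the SAP compares them with an unordered likelihood-ratio chi-square and gives no rule for sparse tables

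*SAP*

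**What the plan says.** SAP 4.4.2 puts each knee in one of three groups at 12 months: a higher K-L grade than at baseline, "no change in grade from baseline to 12 months or (3) Improvement", meaning a lower grade. The comparison of arms "will be done using a Likelihood Ratio Chi-square test", and "This test will also be repeated within subgroups defined by the baseline K-L grade". Table 6 lists this as "Change in K-L by baseline K-L grade", with the test given as "Likelihood Ratio Chi-Square for each subgroup". Table 6 has no expected-outcome column.

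Table 5 in SAP 4.4.1 includes "EQ-5D Dimensions (Mobility, Self-Care, Usual Activities, Pain/Discomfort, Anxiety/Depression) (12 Month"), tested by the likelihood-ratio chi-square with APS Superior as the expected outcome. A second row repeats the test at 1, 3 and 6 months, where the expectation is a trend in favour of APS. The protocol synopsis (Clinical Assessment Tools) says the EQ-5D-3L covers its five dimensions, ending with "anxiety/depression over three levels of" severity.

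The only substitution rule, in SAP 4.1, concerns T-tests (Satterthwaite or Wilcoxon Mann-Whitney). It does not reach the chi-square tests. All these analyses are exploratory at an unadjusted alpha of 0.05.

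**The concern.** Both outcomes run from better to worse. A 2-df likelihood-ratio chi-square gives the same p-value however the three columns are arranged. Three things follow.

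- **Direction.** Table 5 asks whether APS is better, but this p-value answers only whether the two distributions differ in any way.
- **Power.** If the effect is a shift along the scale, spreading it over 2 df wastes information. Ignoring the subject's baseline level on the same dimension wastes more.
- **Size.** The chi-square approximation is doubtful when a category is rare. K-L improvement within 12 months may well be rare, and splitting by baseline grade thins the tables further. Protocol inclusion criterion 3 admits grades 2 to 4. A grade 4 knee cannot worsen, so that subgroup has only two possible categories.

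At stake is how clearly 20 EQ-5D dimension tests (5 dimensions at 4 visits) and the K-L comparisons can be read.

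**Working it through.** **Inputs from the documents.** Two arms, 1:1; three ordered categories; alpha 0.05. Arm size is taken as the 93 evaluable per group in SAP 6.1. The planned 123 per group less 25% attrition gives 123 × 0.75 = 92, so 93 is a fair working size. The documents give no power or size figure for these tests, so there is none to reproduce. (As a separate matter, 93 does not follow from Table 15's difference of 2.27 and pooled SD of 4.06 at alpha 0.049 and 90% power. Those give 69 by the exact t calculation; 93 needs the saline SD of 4.73. Nothing below depends on this.)

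**Inputs assumed.** K-L change rates, EQ-5D level rates and K-L subgroup sizes are not in the documents. They are assumed and varied.

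**Tests compared.**
- Planned: G = 2 Σ O ln(O/E), referred to chi-square on (2−1)(3−1) = 2 df, with fewer df if a column is empty.
- Ordered: Q = (T − n(N+1)/2)² / V on 1 df. T is the sum of midranks r in one arm of size n, N = 2n, and V = n²/(N(N−1)) × Σ(r − mean r)². This is the Wilcoxon or row-mean-score test.

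**Cost of the extra df.** For 80% power at 0.05, the noncentrality needed is 7.85 on 1 df and 9.63 on 2 df. A pure shift with 80% power on 1 df has 71% on 2 df. Recovering it takes 9.63/7.85 = 1.23, or about 23% more patients.

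**Power and direction, 93 per arm, simulated tables.** Percentages are worse/same/improved for K-L and best/middle/worst level for EQ-5D.

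| Scenario (assumed) | Planned | Ordered |
|---|---|---|
| EQ-5D dimension, 42/52/6 v 28/60/12 | 52% | 61% |
| EQ-5D, proportional odds, OR 2, several baselines | 52–62% | 59–72% |
| K-L, both ends shift, 6/87/7 v 15/82/3 | 55% | 64% |
| K-L, proportional odds, OR 2 | 36–41% | 44–50% |
| K-L, only worsening differs, 6/91/3 v 15/82/3 | 45% | 40–42% |
| K-L, only worsening differs, 10/85/5 v 20/75/5 | 40% | 36% |
| K-L, only worsening differs, 8/90/2 v 20/78/2 | 59% | 60% |
| No net shift, 10/85/5 v 20/65/15 | 85% | about 5% |

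In the last row one arm has more worsening and equally more improvement. The planned test is significant 85% of the time although neither arm is better on balance.

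**Baseline level.** With a latent correlation of 0.5 between the baseline and 12-month level (assumed), power was 55% unordered, 64% ordered, and 71% ordered with stratification by baseline level. A second simulation with a different baseline distribution gave 50%, 60% and 66%. Stratifying therefore adds about 6 to 7 points at that correlation. With zero correlation it adds nothing.

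**Size of the planned test under no effect** (K-L worse 5–20%, improved 1–5%):

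| Per arm | Size, planned test |
|---|---|
| 93–123 | 5.6–6.6% |
| 30–60 | 5.6–7.5% |
| 20 | 4.2–6.9% |
| 10 | 1.3–7.3% |

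It exceeds 5% in 31 of 35 scenarios. It falls well below in the sparsest, for example 1.3% with 5/94/1 at 10 per arm. For a grade 4 subgroup (2x2 table, exact enumeration), size is 9.1% at 40 per arm with 5% improved, but 0.1 to 4.1% with 2% improved at 10 to 40 per arm. For EQ-5D dimensions it is 4.9–6.5%. The ordered test stays at 4.5–5.0% for 93–123 per arm and 3.7–5.0% for 30–60, and is conservative below that.

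**The case against.** The case for leaving the plan alone has real force on K-L.

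- A reader might infer that an ordered test is always more powerful. It is not. K-L improvement may be rare, so a difference confined to worsening is a natural scenario. There the ordered test is level or a few points behind, even though such a difference is a consistent benefit.
- A reader might infer that the K-L test generally rejects too often. Excess is common under the assumed rates but mostly modest, and it reverses in very sparse tables. The documents give no rates or subgroup sizes that would settle which applies.
- A reader might infer that the K-L test fails a stated superiority aim. Table 6 states none, and section 4.4.2 asks only about the percentage in each category. The superiority expectation belongs to the EQ-5D rows of Table 5.
- Direction can be read from category percentages shown by arm. It is the p-value alone that lacks it.
- Directional comparisons of related constructs are already planned: EQ VAS and EQ-5D index by T-test or Wilcoxon in Table 5, and joint space width and narrowing in Table 6.

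All of this stands. It confines the power argument mainly to EQ-5D and makes the size argument conditional. It does not answer the mismatch between an unordered test and the Table 5 superiority aim, the neglect of baseline level, or the lack of any sparse-table rule.

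**Conclusion.** The point holds as a low-impact improvement. That the outcomes are ordered, that the test ignores the order, and that no fallback covers it are plain from the SAP and protocol. For a shift across levels the loss is about 3 to 10 points of power at 93 per arm, with roughly 6 to 7 more from ignoring baseline level if the correlation is about 0.5. For K-L change, a gain needs movement at both ends of the scale. The size of the planned test in sparse K-L tables is unreliable rather than uniformly inflated. These figures rest on assumed category rates.

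It would be wrong to infer that any main conclusion of the trial is threatened. The tests sit outside the fixed sequence, are labelled exploratory and are openly unadjusted for multiplicity.

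**What to change.** **EQ-5D dimensions (Table 5, all four visits).** Replace the likelihood-ratio chi-square with a Cochran-Mantel-Haenszel row-mean-score test stratified by baseline level, or a proportional-odds model with baseline level as covariate. Report the common odds ratio with its 95% confidence interval, so that the result has a direction and a size.

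**K-L change (section 4.4.2 and Table 6).** Use a Wilcoxon or row-mean-score test overall and within baseline grade, with exact p-values in the subgroups. Treat baseline grade 4 as a 2x2 table (unchanged v improved) with Fisher's exact test. Show category percentages by arm.

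**Cost.** SAP wording and modest programming; no new data. Rank and exact methods are already in the plan. The price is a small loss of power when the difference lies in one category only and, if the model is chosen, a proportional-odds assumption fitted for five dimensions at four visits. The stratified row-mean-score test avoids that assumption for the p-value.

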#### Table 6 - Planned Statistical Tests for X-ray Results

Mean JSW at 12 Months	T-Test or WMW
Mean JSN (12 months minus baseline)	T-Test or WMW

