### 1.3 Randomization

Subjects will be randomized to either the APS or HA treatment group on a 1:1 basis. The subjects and investigators will both remain blinded throughout Phase I of the study. Assignment to treatment groups will be stratified by site and will use random block sizes. Specifically, designated unblinded personnel at each site will provide the masked syringe to the injecting health care provider. To protect the double-blind, the treating health care professional and evaluating health care professional will be different individuals. Assignment will not be revealed until after the blood has been drawn for nSTRIDE APS Kit processing.

The randomization plan will be produced using SAS v 9.4 or similar software. Balanced randomization with random block sizes (1:1, APS: HA) will be implemented. In the event that, post-randomization, no study treatment was given, randomization will not be reassigned; however, this case will not count toward the overall sample size. Randomization will continue with the next case enrolled until the minimum sample size is reached in both treatment groups. Randomization will be stratified by site, and each site will receive separate randomization plans using random predetermined block sizes that will remain undisclosed to the sites. The randomization file will be uploaded into the electronic data capture (EDC) system. Once the subject is enrolled into the EDC and has been identified as eligible for randomization, the randomization allocation will be visible within the EDC and viewable only by the unblinded research associate. The subject will be treated according to the contents of the displayed randomization allocation.

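### Table 6 tests raw 12-month joint space width without the baseline film; one baseline-adjusted comparison per compartment would be more precise at no cost (minor, exploratory)

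*SAP*

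**What the plan says.** SAP Section 4.4.2 gives the purpose of the measurement: "Measurements of medial and lateral Joint Space Width (JSW) will be performed to assess narrowing over time". It defines JSN as "calculated for each compartment as the change in JSW between the 12 Month visit and the Baseline visit".

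Table 6 then lists two tests based on JSW, each by t-test or WMW: "Mean JSW at 12 Months" and "Mean JSN (12 months minus baseline)". Neither is a baseline-adjusted model. All imaging tests are run at 0.05 and "will not be adjusted for multiple comparisons as these are exploratory outcomes".

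Other relevant places:
- SAP Section 1.3: "Randomization will be stratified by site". No other stratification factor is named.
- SAP Section 2, Table 1: balance is checked for gender, age, BMI, race and WOMAC pain. JSW and K-L grade are not listed.
- SAP Section 6, Per Protocol: exploratory efficacy endpoints use the per-protocol set without imputation.
- Protocol synopsis, Inclusion Criteria: K-L grades 2 to 4 are eligible, with severe osteoarthritis excluded.
- Protocol synopsis, Exploratory Endpoints: JSN, its relation to NRS pain and to OMERACT-OARSI status, and change in K-L grade are listed. Raw JSW is not.

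**The concern.** The stated aim is narrowing over time, but one of the two JSW rows makes no use of the starting width. Subjects enter with different joint widths, and allocation does not balance the arms on width or K-L grade. A raw 12-month comparison therefore carries all of the entry variation as noise, and any chance difference in entry width between the arms passes into the result. Table 1 would not bring such a difference to light.

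At stake is the reading of the structural result. The raw row could show a nominal arm difference that was already there at entry, or show nothing where the JSN row shows a difference. Table 6 does not say which row is to be preferred if they disagree.

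**Working it through.** The plan gives no power, SD or correlation for JSW, so there is no imaging figure to reproduce. The check is of relative precision.

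**Inputs**
- 93 per arm: the evaluable number in SAP Section 6.1, used for illustration. The number with usable films is not stated.
- Two-sided alpha 0.05 (SAP Section 4.4.2).
- Assumed: the same SD *s* at both visits, *s* = 1.0 to 1.5 mm, and baseline to 12-month correlation *r* = 0.80 to 0.95. Lower *r* is shown for range.

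**Variance per subject**
- Raw 12-month JSW: s²
- Change score (JSN): 2s²(1 − r)
- ANCOVA on baseline: s²(1 − r²)

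**Sample-size ratios**
- Raw to ANCOVA: 1/(1 − r²)
- Change score to ANCOVA: 2(1 − r)/(1 − r²) = 2/(1 + r)

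| r | raw / ANCOVA | change / ANCOVA |
|---|---|---|
| 0.50 | 1/0.75 = 1.33 | 2/1.50 = 1.33 |
| 0.70 | 1/0.51 = 1.96 | 2/1.70 = 1.18 |
| 0.80 | 1/0.36 = 2.8 | 2/1.80 = 1.11 |
| 0.90 | 1/0.19 = 5.3 | 2/1.90 = 1.05 |
| 0.95 | 1/0.0975 = 10.3 | 2/1.95 = 1.03 |

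**Difference detectable with 80% power.** The standard error of the raw difference is s × √(2/93) = 0.147s, and the detectable difference is 2.8 × SE = 0.41s.
- Raw: 0.41 mm (s = 1.0) to 0.62 mm (s = 1.5), whatever *r* is.
- Change score, factor √(2(1 − r)): 0.41 × 0.316 = 0.13 mm (s = 1.0, r = 0.95) to 0.62 × 0.632 = 0.39 mm (s = 1.5, r = 0.80).
- ANCOVA, factor √(1 − r²): 0.41 × 0.312 = 0.13 mm to 0.62 × 0.60 = 0.37 mm at the same two corners.

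**Power for a true difference of 0.2s, r = 0.9, 93 per arm.** Raw 28%, change score 86%, ANCOVA 88%.

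**Bias.** In 20,000 simulated trials with no effect (r = 0.9, 93 per arm), the mean raw difference was about zero. Type I error was 5.1% for the raw test and 4.9% for the change score.

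**Exposure to a given imbalance.** The 5.1% is an average over all randomisations. Suppose the arms differ at entry by two standard errors, 2 × 0.147s = 0.29s, which happens by chance about once in twenty trials. With r = 0.9 and no effect:
- expected raw 12-month difference: 0.9 × 0.29s = 0.26s
- its conditional SE: √(1 − 0.81) × 0.147s = 0.064s
- rejection threshold: 1.97 × 0.147s = 0.29s
- chance of a false rejection: about 35%

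ANCOVA removes this dependence on the entry difference.

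**JSN is not lost.** JSN is 12-month JSW minus baseline JSW. With baseline JSW in the model, taking JSN as the outcome instead of 12-month JSW lowers the baseline coefficient by 1 and leaves the treatment coefficient and its CI unchanged.

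**The case against.** The strongest reply is that the next row of Table 6 already does the job. It tests change from baseline, and Section 4.4.2 defines JSN per compartment. The protocol names JSN and not raw JSW, so the documents themselves point to JSN as the structural measure. Measured against that row, ANCOVA saves only 3% to 11% in sample size (power 86% against 88% in the example). The endpoint is exploratory, and replacing t-test or WMW by ANCOVA alone would drop the rank-based option. All of this stands. It limits the point to one weak, redundant row and a small gain over the other.

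Stronger readings that a reader might infer are not supported:
- *That Table 6 cannot show narrowing.* The JSN row tests it. Between randomised arms, the expected difference in 12-month means also equals the expected difference in change, so even the raw row estimates the right quantity, only poorly. Per-protocol exclusions could weaken that argument, but they are settled by blinded review and nothing in the documents shows them to differ by arm.
- *That the raw result mainly reflects width at entry.* Entry width explains r² of the 12-month variance, which exceeds half only if *r* is above about 0.71. No correlation is given. Nor do the documents give a figure for the spread of entry widths, and severe disease is excluded.
- *That a real structural effect would be missed.* The JSN test would detect it almost as often as ANCOVA when *r* is high.

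**Conclusion.** The point holds as a minor one. The raw 12-month JSW test is valid on average but imprecise, open to chance imbalance at entry, and adds little beside JSN. With an assumed correlation of 0.80 to 0.95 it needs 2.8 to 10.3 times the subjects of a baseline-adjusted test, against 1.03 to 1.11 times for the planned change score. These ratios rest on the assumed correlation and on equal SDs at the two visits; the millimetre figures also rest on the assumed SD and on 93 per arm. At lower correlation the raw row loses less and the change score loses more (both 1.33 at r = 0.5), and ANCOVA is at least as precise as either throughout. No success criterion and no step of the fixed testing sequence depends on it.

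**What to change.** In Section 4.4.2 and Table 6, for each compartment:
1. Make the between-arm JSN comparison an ANCOVA of 12-month JSW (or, equivalently, JSN) on treatment and that compartment's baseline JSW. Report the adjusted arm difference with its 95% CI.
2. Keep a rank-based fallback for extreme non-normality, for example rank ANCOVA, and state when it applies. The switching rule in Section 4.1 names Tables 4 and 5 only.
3. Report raw 12-month JSW descriptively by arm, without a test.

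The cost is one model line and a sentence on the fallback. No new data are needed, since JSN already requires the baseline JSW, and subjects without a baseline film are already absent from the JSN row.
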